7 SAMPLE SIZE AND STATISTICAL ANALYSIS

7.1 Sample Size Calculation

The two tests hhCG and hCG+ β will be compared using receiver operating characteristics (ROC) curves by analyzing the area under the curve (AUC). Based on the data by Chuan S et al. [16], an AUC of 0.67 is assumed for the hCG+ β test and an AUC of 0.79 for the hhCG test. Under the assumption that 45% of all patients with IVF will present with clinical pregnancy on day 21* (+4/-3), 136 patients are necessary to achieve 80% power for a one-sided z-test with significance level alpha = 2.5%.

Power	N+ *	N- **	AUC1	AUC2	Correlation
0.8022	61	75	0.6700	0.7900	0.6

* Pregnancies

** No Pregnancies

The results are for tests with continuous values and are based on the methodology of Hanley and McNeil (1983). The calculations are further based on the binormal model and the assumption of a correlation of 0.6 between the two tests for both the positive and negative groups (N+ and N-). Allowing for 10% of patients being non-evaluable, 152 patients are planned to be enrolled.

*Counted from ET (=Day 0).

7.2 Targeted Accrual

The 152 patients are planned to be enrolled over a period of 9 months, from June 1, 2017 at the earliest to February 28, 2018.

7.3 Groups for Biostatistical Analysis

The population of **patients enrolled** will include all patients who gave informed consent.

The **patients treated** population will consist of all patients for whom the IVF-ET was performed.

The per-protocol population will consist of all eligible patients treated, i.e. will be restricted to those patients of the **patients treated** population who did not violate any eligibility criteria and who have available measurements for both hhCG and hCG+ β on day 4* (+1) and an assessment of clinical pregnancy on day 21* (+4/-3). A missing assessment of clinical pregnancy on day 21 (+4/-3) can be replaced by an assessment of ongoing pregnancy on day 28 (+4/-3) and/or 65 (+7).

In case of sufficiently high numbers of multiple pregnancies, subgroup analyses may be performed for patients with multiple and single pregnancies. Further subgroups of interest, if any, will be defined in the Statistical Analysis Plan.

*All days mentioned in this section are counted from ET (=Day 0).

7.4 General Biostatistical Approaches

For the pregnancy tests based on hCG and hCG+ β levels, ROC analyses will be performed. The predicted results of the test (positive or negative, i.e. pregnant or not pregnant) will be compared to the actual presence/absence of pregnancy as observed (e.g. clinical pregnancy on day 21* (+4/-3) or ongoing pregnancy on day 65 (+7)). There are the following possibilities for the test results and observed results:

		Observed	
		Positive	Negative
Test	Positive	True positive (TP)	False positive (FP)
	Negative	False negative (FN)	True negative (TN)

For the test concerned, the rate of true positives and true negatives can be regarded in two different ways: in relation to the observed positives and negatives and in relation to the predicted positives and negatives.

Based on the observed positives and negatives, the rate of true positives is called the **sensitivity** and the rate of true negatives is called **specificity**, i.e.:

$$\text{Sensitivity} = \text{TP} / (\text{TP} + \text{FN})$$

$$\text{Specificity} = \text{TN} / (\text{TN} + \text{FP})$$

Based on the predicted positives and negatives, the rate of true positives is called the **positive predictive value (PPV)**, and the rate of true negatives is called the **negative predictive value (NPV)**, i.e.:

$$\text{PPV} = \text{TP} / (\text{TP} + \text{FP})$$

$$\text{NPV} = \text{TN} / (\text{FN} + \text{TN})$$

Sensitivity, specificity, positive and negative predictive values are all dependent on the definition of the test concerned. Receiver operating characteristics (ROC) curves are used to visualize sensitivity and specificity for various thresholds for the pertinent test: Sensitivity is plotted against 1-specificity and thus displays the test's characteristics for various cut-offs. Tests can be compared by looking at summary measures for the ROC curves, e.g. the area under the curve (AUC). Since high sensitivity and specificity are wanted in a test, a bigger area under the curve is desirable.

To define a test for practical use, a threshold has to be chosen, i.e. a cut-off that defines that values below are considered as negative test results and values above as positive test results. A threshold should be chosen as a point that optimizes the combination of sensitivity and specificity which can be done via the ROC curve by choosing the point with the least distance to the upper left corner which stands for specificity = 100% and sensitivity = 100%.

All other data will be summarized by descriptive statistics in case of continuous variables or by absolute and relative frequencies. Laboratory data will be displayed over time for each visit as will ultrasound results. Concomitant diseases and medications will be listed for the complete

duration of the study. Incidents and indirect harms will be summarized by absolute and relative frequencies.

*Counted from ET (=Day 0).

7.5 Descriptive Statistics

Continuous variables will be summarized by descriptive statistics (mean, standard deviation, median, Q1, Q3, minimum, maximum, number of available data); categorical variables will be summarized by absolute and relative frequencies and number of available data. The relative frequencies will be based on the number of available data if not mentioned otherwise.

7.6 Analysis by Study Objectives

7.6.1 Primary study Objective

The primary study objective is to determine, based on the AUCs of the ROC curves, whether serum hyperglycosylated human chorionic gonadotropin (hhCG) measured on day 4 (+1) after embryo transfer (ET) is superior to hCG+ β measured on day 4* (+1) in predicting clinical pregnancy on day 21* (+4/-3) (=6 weeks after last menstruation, detection of embryo sac by US).

The empirical AUCs, pertinent standard errors and 95% confidence intervals will be estimated for both the hhCG test and the hCG+ β test. Furthermore, the empirical AUCs of the two tests will be compared using a logistic regression model and the difference in AUCs will be estimated including 95% confidence intervals and chi-square test for the contrast. hhCG measured on day 4 (+1) after ET is considered superior to hCG+ β if the null hypothesis

$$H_0: \text{AUC (hhCG)} \leq \text{AUC (hCG+}\beta\text{)}$$

can be rejected at an one-sided significance level of 0.025.

The empirical ROC curves will be plotted to provide a visualization that supports the comparisons.

*Counted from ET (=Day 0).

7.6.2 Secondary Study Objectives

In addition to the comparison of the AUCs under the ROC curves for day 4*, the same analyses will be performed for the hhCG and hCG + β tests at days 7 and 11 with respect to predicting clinical pregnancy on day 21*; at days 4, 7 and 11 with respect to predicting pregnancy on day 65; at days 4 and 7 with respect to predicting pregnancy on day 11. The same methods as for the analysis of the primary objective will be applied here.

For the comparisons of sensitivity and specificity and the positive and negative predictive values at various time points with respect to pregnancy at various later time points, the following approach will be used:

Optimal thresholds for the two tests and the various time points will be identified from the pertinent ROC curves for the time point (day 4, 7 or 11) and endpoint (pregnancy at day 65,

21 or 11) considered. The optimal threshold for the time point and test at hand will be found using Youden's index (sensitivity + specificity -1), choosing the point for which the index is maximal.

The thresholds and the corresponding sensitivities and specificities will be summarized for each time point, pregnancy endpoint and test. Pertinent positive and negative predictive values will be shown for the same thresholds for the various time points.

The course of hhCG and hCG + β over time will be summarized by descriptive summary statistics (mean, standard error of the mean, median, Q1, Q3, minimum and maximum) for the disjoint pregnancy outcome categories as defined in 5.1. If there are sufficiently many multiple pregnancies, the same analysis will be performed for the categories of multiple and single pregnancies (irrespective of pregnancy outcome).

Incidents and indirect harms will be summarized by absolute and relative frequencies.

*All days mentioned in this section are counted from ET (=Day 0).

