PRIMARY PURPOSE	Utility of the hhCG assay (Quest Diagnostics), early after In Vitro Fertilization and fresh or frozen Embryo Transfer (IVF-ET), as aid in the prediction of ongoing pregnancy
STUDY OBJECTIVES	
Primary objective:
 
To determine, based on the AUCs of the ROC curves, whether serum hyperglycosylated human chorionic gonadotropin (hhCG) measured on day 4 (+1) after ET* is superior to hCG+β measured on day 4 (+1) in predicting clinical pregnancy on day 21 (+4/-3) (=6 weeks after last menstruation, with detection of embryo sac by US).
 
*ET= Embryo Transfer; all days mentioned in the following are counted from ET (=Day 0).

	
Secondary objectives*:
 
 1. To determine, based on the AUC of the ROC curves, whether hhCG measured on day 7 (+1) and day 11 (+2) is superior to hCG+β measured on the same days in predicting clinical pregnancy on day 21 (+4/-3) 2. To determine, based on the AUC of the ROC curve, whether hhCG measured on day 4 (+1), day 7 (+1) and day 11 (+2) is superior to hCG+β measured on the same days in predicting ongoing pregnancy on day 65 (+7) . 3. To determine, based on the AUC of the ROC curve, whether hhCG measured on day 4 (+1) and day 7 (+1) is superior to hCG+β measured on the same days in predicting pregnancy on day 11 (+2) defined by serum hCG+β. 4. To compare the sensitivity and specificity and the positive and negative predictive value of hhCG with hCG+β measured on days 4 (+1), 7 (+1) and 11 (+2) for clinical pregnancy on day 21 (+4/-3) and ongoing pregnancy on day 65 (+7) and to identify cut-off values. 5. To compare the sensitivity and specificity and the positive and negative predictive value of hhCG with hCG+β measured on days 4 (+1) and 7 (+1) for pregnancy on day 11 (+2) defined by serum hCG+β and to identify cut-off values. 6. To determine, based on the AUCs of the ROC curves, whether changes in hhCG on day 7 (+1) vs. day 4 (+1) and day 11 (+2) vs. day 7 (+1) are superior to corresponding

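### Seven secondary AUC comparisons appear to inherit the primary's one-sided 0.025 superiority rule and five change-score objectives have no rule; none has multiplicity control or an exploratory label

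*Combined protocol and SAP*

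**What the plan says.** Section 7.6.1 sets one primary hypothesis, with its rule worded for day 4 only: "hhCG measured on day 4 (+1) after ET is considered superior to hCG+ β if the null hypothesis" (AUC of hhCG no larger than that of hCG+β) "can be rejected at an one-sided significance level of 0.025". The method there consists of empirical AUCs with standard errors and 95% confidence intervals, an estimated AUC difference, and a chi-square test of the contrast.

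Section 7.6.2 then extends the analysis to three groups of comparisons:

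- two for clinical pregnancy, using the day-7 and day-11 samples;
- three for ongoing pregnancy, where the assays are compared "at days 4, 7 and 11 with respect to predicting pregnancy on day 65";
- two for day-11 pregnancy, using the day-4 and day-7 samples.

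It closes the list with "The same methods as for the analysis of the primary objective will be applied here".

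The synopsis words these as superiority questions. Secondary objective 1 asks "whether hhCG measured on day 7 (+1) and day 11 (+2) is superior to" hCG+β, and objectives 2 and 3 follow the same pattern. Objectives 6 and 7 ask it again for changes between visits. Section 2.5.2 names AUCs of changes as secondary endpoints 7 to 9, but the AUC paragraph of 7.6.2 does not mention changes.

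The document contains no adjustment for multiple tests, no order of testing, no link from the secondary tests to the primary result, and no statement that they are exploratory. Section 7.3 defers only the definition of further subgroups to a Statistical Analysis Plan.

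**The concern.** A plan that asks the same superiority question many times, each at the primary's level, gives many chances of a favourable answer. Without a rule on what a secondary result may support, a report could describe hhCG as superior for some day and endpoint when that result is the one chance finding among several.

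Two features make this more than a formality. First, the title, the indication and the primary purpose concern ongoing pregnancy, while the primary test concerns clinical pregnancy on day 21. Everything the study can say about hhCG's superiority for ongoing pregnancy therefore comes from secondary comparisons: three under objective 2 and two change-score comparisons under objective 6.

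Second, no difference is a realistic state of affairs for some of these tests. Section 1.2.1 reports that, in the retrospective study used for the sample size, the two assays performed similarly on day 16 after retrieval, which is day 11 after transfer. The plan nevertheless poses a day-11 superiority question for clinical and for ongoing pregnancy.

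**Working it through.** **1. The plan's own figure.** The document states no error rate for the secondary family. Its only related figure is the power of the primary test in 7.1: 0.8022 with 61 pregnant and 75 non-pregnant patients, AUCs 0.67 and 0.79, marker correlation 0.6, one-sided 2.5%.

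- Hanley-McNeil variance: [A(1−A) + (61−1)(Q1−A²) + (75−1)(Q2−A²)]/(61×75), with Q1 = A/(2−A) and Q2 = 2A²/(1+A).
- A = 0.67 gives 0.002203 (SE 0.0469). A = 0.79 gives 0.001598 (SE 0.0400).
- A marker correlation of 0.6 corresponds to a correlation between the two AUCs of about 0.56 (binormal simulation) to 0.57 (binormal covariance).
- At r = 0.57, the SE of the difference is √(0.002203 + 0.001598 − 2×0.57×0.0469×0.0400) = 0.0408. The null SE at AUC 0.67 is √(2×0.002203×0.43) = 0.0435.
- Power = Φ[(0.12 − 1.96×0.0435)/0.0408] = Φ(0.851) = 0.803. At r = 0.56 it is 0.793.

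This agrees with 0.8022. Other variance formulas give up to about 0.87. The calculation covers one test only, so the secondary comparisons play no part in the stated 2.5% or 80%.

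**2. Count of superiority questions.**

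| Source | Comparisons | Covered by 7.6.2 |
|---|---|---|
| Objective 1 (days 7, 11; clinical pregnancy) | 2 | yes |
| Objective 2 (days 4, 7, 11; ongoing pregnancy) | 3 | yes |
| Objective 3 (days 4, 7; day-11 pregnancy) | 2 | yes |
| Objective 6 (2 changes × 2 endpoints) | 4 | no |
| Objective 7 (1 change; day-11 pregnancy) | 1 | no |

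The total is 12. Seven have a method carried over from the primary, and five have a superiority objective without a stated test or threshold.

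**3. Chance of at least one false superiority finding among the seven, all nulls true, each at one-sided 0.025.**

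- Independent tests: 1 − 0.975⁷ = 1 − 0.8376 = 16.2%, or 16.2/2.5 = 6.5 times nominal. The tests share patients, repeated assays and overlapping outcomes, so independence overstates the figure.
- Equal pairwise correlation ρ between the seven statistics: 1 − ∫φ(x) Φ[(1.96 − √ρ·x)/√(1−ρ)]⁷ dx.

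| ρ (assumed) | 0.2 | 0.5 | 0.7 | 0.9 |
|---|---|---|---|---|
| Any false finding | 14.7% | 11.5% | 8.9% | 5.7% |

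- Simulation of DeLong contrasts with 136 patients, 3,000 runs per row, and an assumed day-to-day correlation within each assay:

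| Day-to-day correlation (assumed) | Single-test error | Mean correlation of the seven statistics | Any false finding |
|---|---|---|---|
| 0.2 | 2.6% | 0.25 | 12.6% |
| 0.5 | 2.3% | 0.39 | 10.4% |
| 0.8 | 2.4% | 0.60 | 8.9% |

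The simulation error is about √(0.104×0.896/3000) = 0.6 percentage points. The single-test column confirms that each test alone stays near 2.5%. The simulated range of 8.9% to 12.6% is 3.6 to 5 times nominal.

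**4. The five change-score comparisons.** No error rate can be computed from the plan, because it gives them no decision rule. If they were also tested at 0.025, the figure for twelve tests would be 1 − 0.975¹² = 26.2% under independence and 16.4% to 19.5% in the same simulation. That is an assumption about an unwritten rule.

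**The case against.** The strongest defence is that the plan is disciplined where it counts. It names one primary endpoint (2.5.1), one hypothesis with its own level (7.6.1) and a sample size built on that test alone (7.1). The study is a proof of concept (1.2.2, 2.1.2), and hhCG results are withheld until after study completion, so they cannot affect care. In that setting, strict familywise control over secondary endpoints is not obligatory. The decision rule in 7.6.1 is worded for day 4, so the carry-over sentence in 7.6.2 could mean only the estimation and contrast methods. The correlations behind any realistic error figure are not in the document.

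Much of this stands. Carry-over of the 0.025 rule is an inference, although the superiority wording of objectives 1 to 3 makes it the natural one. The error figures rest on assumed correlations. Proof-of-concept status lowers the stakes, but it would settle the matter only if the plan called these comparisons exploratory, which it does not.

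A reader might infer that all twelve comparisons carry the primary's rule, so that the relevant figure is 26.2%. Section 7.6.2 does not support that: it lists seven. A reader might also infer that the stated 2.5% no longer describes the trial's conclusion, or that a secondary finding may replace a failed primary. No section says so. The primary test is single and keeps its level. The gap is that the plan does not say what a secondary result may be used to conclude.

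**Conclusion.** The point holds for the secondary comparisons and does not touch the primary conclusion. Seven secondary AUC comparisons appear to inherit a superiority rule at one-sided 0.025, five more superiority objectives have no test or threshold, and nothing controls or limits the claims drawn from any of them. With no true differences, the chance of at least one false superiority finding among the seven is about 9% to 13%, against 2.5% for any one test. The bounds are 16.2% under independence and 5.7% if the statistics were correlated at 0.9.

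This rests on three assumptions: that the 0.025 rule travels with the methods, that all seven nulls are true together, and that the correlations lie in the range tried. Any multiplicity text in a separate analysis plan is outside the document reviewed. A wording change before hhCG results are available is a cheap improvement, particularly because the ongoing-pregnancy question depends wholly on secondary comparisons.

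**What to change.** Add to 7.6.2: 'The only confirmatory superiority conclusion of this study is the primary comparison (day 4, clinical pregnancy). All secondary AUC differences, including those for changes between visits, are exploratory. They will be reported as estimates with unadjusted 95% confidence intervals and without a superiority conclusion.' This also supplies the missing analysis statement for objectives 6 and 7.

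Reword secondary objectives 1, 2, 3, 6 and 7 in the synopsis from asking whether hhCG is superior to estimating the difference in AUC, so that the synopsis and 7.6.2 agree.

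If the sponsor wants a confirmatory claim for ongoing pregnancy, it may optionally name one such comparison, to be tested at one-sided 0.025 only after the primary null is rejected. That choice should be fixed before hhCG results are available. A Bonferroni split would be dearer. At 0.025/7 = 0.0036, a secondary comparison with the primary's assumed effect and precision would have power of about 0.55 instead of 0.80.

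The cost is an amendment to protocol wording, with no added patients, samples or assays and no loss of primary power. The downside is that an isolated favourable secondary result cannot be called superior.

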1.2 Background and Study Rationale

1.2.1 Background

Hyperglycosylated human chorionic gonadotropin (hhCG) as it was later called was first isolated from the urine of women with invasive trophoblastic disease [2]. It is a hyperglycosylated isoform of human chorionic gonadotropin (hCG) with more extensive and more complex carbohydrate moieties than hCG during the initial 3 weeks of pregnancy hhCG is the primary hCG isoform [3–9]. It is synthesized primarily by cytотrophoblasts, whereas hCG is produced by syncytiotrophoblasts [12, 13]. hhCG is supposed to be of relevance during implantation into the uterine wall [13–15]. The monoclonal antibody against hhCG, B152, has a specificity for hhCG of >99 % relative to hCG [4, 8, 10], whereas many other antibodies against hCG show significant cross reactivity with hhCG [11].

Urinary hhCG levels during pregnancy were shown to rise 3 days sooner on average than those of hCG. The ratio of hhCG to hCG may allow to differentiate between clinical and biochemical pregnancy [5].

In a retrospective monocenter evaluation in 112 women with in vitro fertilization (IVF), fresh embryo transfer (ET) and day-9 and day-16 after egg retrieval (equals days 4 and 11 after ET) serum samples carried out by Chuan et al. it was found that a day-9 hhCG level of >110 pg/mL was 96% specific for ongoing pregnancy, yielding a positive predictive value of 94%. Compared with the day-9 hCG level, hhCG was more sensitive and had a larger area under the curve (0.87 vs. 0.67, respectively). In contrast, the diagnostic test characteristics were similar between the day-16 hhCG and hCG levels [16]. In a prospective blinded clinical trial by Strom et al. enrolling 58 IVF-ET patients a single serum or urine hhCG measurement identified pregnancies (both biochemical and clinical) on day 6 post ET with 100% sensitivity and specificity, whereby it was possible to identify biochemical pregnancies by their lower hhCG values [17].

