1.2.2 Study Rationale

Proceeding on the results of previous clinical studies and particularly of the two studies by Chuan and Strom mentioned above [16, 17], it is a logical further step to try and validate the hypothesis of a superior predictive value of hhCG vs. hCG early after IVF-ET for clinical and ongoing pregnancy in a prospective study sufficiently powered based on existing data for the two diagnostic tests. The nature of the study is therefore that of a proof of concept trial.

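### Section 7.6.2 reports hhCG accuracy only at thresholds chosen from the study's own data and never at the published day-4 cut-off cited in the background

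*Combined protocol and SAP*

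**What the plan says.** Section 1.2.1 describes the cited study as follows: "In a retrospective monocenter evaluation in 112 women with in vitro fertilization (IVF), fresh embryo transfer (ET"). It reports that "a day-9 hhCG level of >110 pg/mL was 96% specific for ongoing pregnancy, yielding a positive predictive value of 94" per cent, and that day-9 hhCG "had a larger area under the curve (0.87 vs. 0.67, respectively") than hCG. The section equates day 9 after retrieval with day 4 after transfer, which is Visit 1 here.

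Section 1.2.2 gives the aim: to "validate the hypothesis of a superior predictive value of hhCG vs. hCG early after IVF-ET for clinical and ongoing pregnancy". Section 7.6.1 tests this by comparing AUCs. Superiority of day-4 hhCG is claimed if the null hypothesis "can be rejected at an one-sided significance level of 0.025".

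Secondary objectives 4 and 5 in the synopsis add accuracy measures and the identification of cut-offs. Section 7.6.2 carries these out: "Optimal thresholds for the two tests and the various time points will be identified from the pertinent ROC curves", using the maximum Youden index. PPV and NPV are shown at those same thresholds. The value >110 pg/mL does not reappear in any objective, endpoint or analysis.

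**The concern.** Two things follow from taking every hhCG threshold from the study's own ROC curves.

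- **Optimism.** The threshold is picked to look best in the patients on whom it is then assessed, so the reported sensitivity and specificity are biased upwards. The plan gives no correction and no caution.
- **A missing fixed reference point.** A cut-off set in advance from another cohort gives accuracy estimates free of threshold selection. The protocol cites one, for the same marker, the same nominal day and an outcome that this study also collects. As written, the tables would not show how it performs.

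The AUC comparison does not fill the gap. It shows which marker ranks women better, not the specificity or PPV at a decision point.

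**Working it through.** **1. The plan's own figure.** Inputs from section 7.1: AUC 0.67 and 0.79, 61 pregnant, 75 not pregnant, correlation 0.6, one-sided alpha 2.5%, stated power 0.8022. The Hanley-McNeil standard errors are 0.0469 and 0.0400. Under the binormal model, a correlation of 0.6 between test values gives about 0.57 between the AUCs.

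- Null variance: 2 × 0.0469² × (1 − 0.57), SE about 0.0435.
- Alternative variance: 0.0469² + 0.0400² − 2 × 0.57 × 0.0469 × 0.0400, SE about 0.0408.
- Power: Φ[(0.12 − 1.96 × 0.0435)/0.0408] = Φ(0.85), about 0.80 (0.803 unrounded).

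The stated power is reproduced. The primary comparison needs no cut-off.

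**2. Where the Youden threshold lands.** Assume equal-variance binormal scores with AUC 0.79. The separation is d = √2 × Φ⁻¹(0.79) = 1.14. The Youden point then has sensitivity = specificity = Φ(d/2) = Φ(0.57), about 72%, and a true index of 2 × 0.716 − 1 = 0.43. In 4,000 simulated studies of 61 and 75 women:

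| Quantity at the selected threshold | Result |
|---|---|
| Apparent specificity, mean (95% range) | 74% (53% to 92%) |
| Apparent Youden index, mean | 0.485 |
| True Youden index, mean | 0.415 |

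The optimism is 0.485 − 0.415 = 0.07. The upper end of the specificity range lies below 96%.

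*Limit of this step.* The same model puts sensitivity at 96% specificity at 27% for AUC 0.79 and 44% for AUC 0.87. The published pair implies sensitivity = (0.94/0.06) × 0.04 × (1 − p)/p, where p is the share pregnant in the cited cohort. The documents do not give p. This is 77% at p = 45% and 63% at p = 50%, and p must be at least about 38.5% for it not to exceed 100%. If those shares are near the truth, the cited data do not follow this model, and the Youden point could lie closer to the published one.

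**3. What a table at >110 pg/mL would show.** Intervals are exact (Clopper-Pearson). The ongoing-pregnancy rate on day 65 is not in the documents; 30% to 45% of 136 is assumed.

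| Ongoing rate (assumed) | Negatives | Specificity observed | 95% CI |
|---|---|---|---|
| 45% | 75 | 72/75 | 88.8% to 99.2% |
| 40% | 82 | 79/82 | 89.7% to 99.2% |
| 35% | 88 | 84/88 | 88.8% to 98.7% |
| 30% | 95 | 91/95 | 89.6% to 98.8% |

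For PPV at 45%: true positives 0.766 × 61, about 47; false positives 0.04 × 75 = 3; 47/50 = 94%, CI 83.5% to 98.7%. PPV moves with the pregnancy rate even if accuracy does not. At 30% it would be 0.766 × 0.30/(0.766 × 0.30 + 0.04 × 0.70) = 0.230/0.258, about 89%.

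**4. What shortfall could be detected.** An exact one-sided 2.5% test of 96% specificity with 75 negatives rejects at 67 or fewer true negatives.

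| True specificity | 92% | 90% | 88% | 85% | 80% |
|---|---|---|---|---|---|
| Power | 0.25 | 0.48 | 0.69 | 0.89 | 0.99 |

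**5. Fresh transfers only.** Their number is not given. If half or one third of the negatives were fresh (about 38 or 25), 36/38 gives 82% to 99% and 24/25 gives 80% to 99.9%.

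**The case against.** The best defence is that the plan does what it promises. Section 1.2.2 speaks of validating a superiority hypothesis, not a cut-off, and section 7.6.1 tests that hypothesis with a comparison that is adequately powered on its own assumptions. The objectives ask for cut-offs to be identified, which is what section 7.6.2 does, and section 2.1.2 limits the scope to proof of concept. This stands. A reader might infer that the study fails to deliver a promised validation of the published results, that it can only generate new cut-offs, or that it cannot confirm or refute the cited figures. The documents do not support these readings. The first misstates the aim; the second is true of the threshold analyses but not of the study; the third describes the written analysis, not the data.

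It can also be said that the cut-off may not carry over. The cited cohort had fresh transfers only, whereas this study admits frozen and donor-egg transfers. Visit 1 allows day 5 after transfer. The calibration behind 110 pg/mL is not stated. A different result could reflect any of these. This also stands, and it limits how the table may be read. It does not argue against producing it.

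Finally, the planned ROC plots would let a reader estimate sensitivity near 96% specificity. They would not show which point corresponds to 110 pg/mL.

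Section 7.3 refers to a Statistical Analysis Plan for further subgroups. No separate text of it is among the documents, so a fixed cut-off defined there cannot be excluded.

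**Conclusion.** The point holds as a gap in the secondary analyses. All hhCG accuracy figures would be in-sample and optimistic, by about 0.07 on the Youden index under the planning assumptions. Under the same assumptions they would usually describe an operating point near 72% specificity, far from 96%. That distance rests on the equal-variance binormal model and an AUC of 0.79. The absence of any result at >110 pg/mL does not.

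The added analysis would be informative but limited. It could expose a fall to 85% or below with good power (0.89 or more), but not a fall to 90% (0.48), and less in fresh transfers alone. The primary analysis and the sample size are unaffected. The change is worth making because it is cheap and uses planned data, not because the design is unsound.

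**What to change.** Add to section 7.6.2, before any hhCG results are released:

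- A pre-specified secondary analysis of day-4 (+1) hhCG at >110 pg/mL, giving sensitivity, specificity, PPV and NPV with exact 95% confidence intervals, for ongoing pregnancy on day 65 (the published outcome) and clinical pregnancy on day 21, overall and in fresh transfers.
- A statement that the Youden cut-offs are exploratory and derived in-sample. In the same edit, reconcile the threshold rule: section 7.4 uses the least distance to the upper left corner, section 7.6.2 the Youden index.
- A statement of limits: precision allows only a large shortfall to be shown, and is lower in fresh transfers; PPV depends on the pregnancy rate; interpretation depends on assay calibration, sampling day and population matching the cited study.

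The cost is a short paragraph and one table. No patients, samples or primary alpha are needed. The drawback is that a discrepant result may have no single explanation if comparability with the cited study cannot be established.
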